Economic Evaluation Supplement Aim: To understand the economic impact of the Southwest Hub interventions. We hypothesize that both the NH and ER interventions' reduction in participant suicidal ideation and improved resilience will reduce participant healthcare and other community and personal costs compared to the standard of care of CM alone.

1. Administer a time use survey (e.g. time-logs) and conduct in-person interviews among the project staff and health workers. Using these tools, we will ask staff to recall how they allocated their time and what resources (e.g. supplies, equipment, etc.) they used.
2. Analyze Celebrating Life Apache surveillance system (CL) data for related data points for study participants, including intake and follow-up case management visits. This data counts the number of times study staff visited or attempted to visit study participants, and is key in accounting for the time and financial costs of conducting study visits with participants.

Diversity Supplement Aim: To assess individual characteristics (age, gender, substance use history, mental health status, educational and employment status, family composition) associated with co-occurrence of suicide ideation or attempts and history of opioid use compared with suicide risks alone

Secondary Aims:

2. To examine mediators and moderators of treatment effectiveness and sequencing in order to determine which types and sequence of interventions is best suited for which youth.
3. To assess the acceptability, feasibility and capacity for sustainability of the Hub's key intervention components (Surveillance/Case Management, New Hope and Elders' Resilience) from the perspective of multiple stakeholders as they are implemented across different tribes. This will also include identifying, prioritizing and testing strategies aimed at enhancing the sustainability of tribally implemented suicide prevention programs.

Opioid Data Collection Sub-Study Aim: Explore community beliefs about: a) correlates of risk (i.e., other substance use, mental health status, family, demographic and social factors), b) protective factors (cultural and spiritual factors) and c) behavior functions (i.e., emotional regulation, reinforcement patterns) of opioid abuse in Native American youth through focus groups with the existing Community Advisory Boards from the Hub partners.

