episode with recent suicidal ideation (i.e., index event); and 2) **implementation of a Sequential Multiple Assignment Randomized Trial (SMART)** to inform how to combine and tailor two brief interventions delivered by paraprofessional community mental health workers (CMHWs), with promising pilot data, to prevent further suicidal thoughts and behavior and promote resilience (and decrease long-term risk both due to suicidal behaviors and substance use including opioids); and 3) evaluate what are the cost savings per study participant with the implementation of the Southwest Hub interventions: *NH, ER, NH and ER*. A secondary aim will be to evaluate the acceptability, feasibility and sustainability of the two brief interventions with other Southwest Hub partners, **including the Navajo, San Carlos Apache, Hualapai, and Cherokee nations**, who will have support from the Administrative Core of the Southwest Hub to implement their own local tribal suicide surveillance systems for community-based identification of at-risk youth.

Background on economic evaluation supplemental aim: Little is known about the cost-effectiveness of mental health interventions for Native Americans. Lack of cost-effectiveness evidence is primarily due to lack of scientific evidence on intervention impact as well as obstacles in quantifying the disability burden for suicide ideation using standard metrics. A recent literature review on the cost-effectiveness of suicide and self-harm prevention interventions shows six studies provided high quality evidence and all six interventions were cost-effective. However, none of these focused on addressing suicidality in Native American populations and none included culturally appropriate interventions for this population. Our partners from the White Mountain Apache Tribe have indicated a strong interest in learning about the economic burden of suicide and costs of addressing it in order to inform policy decisions and future implementation and dissemination of these programs in other tribal settings.

As part of the *economic evaluation supplemental aim* we will administer a time use survey (e.g. time-logs) and conduct in-person interviews to assess the costs of the intervention. The rationale for these activities is doing quality control and capturing all the program resources needed to run the HUB interventions.

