For the economic evaluation supplement, we will use all healthcare claims data for each intervention participant (from one year prior to the study period to 12 months post-enrollment--for a total of 2 years of participant claims data) requested from the Indian health Service's electronic health records to assess healthcare expenditures. We will also ask participants about their school performance and work attendance, as well as, some additional items related to time spent participating in the interventions. These new items for participants are included in the assessment battery.

As part of the economic evaluation supplement, we will collect data from staff about their time use and resources use. For this aim, we will ask all project case managers and health providers to collect daily time-logs. The design of the time-log may vary overtime to better fit program needs or activities. But in general, this tool will ask staff to select which of a pre-defined list of activities they conducted each day and for how many hours each activity. In-person interviews with staff will follow a semi-structure design. A survey tool will be used to guide open ended questions and the survey will be modified over-time to fit program activities.

We will also analyze CL data for related data points for study participants, including intake and follow-up case management visits. This data counts the number of times study staff visited or attempted to visit study participants, and is key in accounting for the time and financial costs of conducting study visits with participants.

For the diversity supplement, we will compare individual characteristics associated with co-occurrence of suicide ideation or attempts and opioid use vs. suicide ideation/attempt without concurrent opioid use risk. We will use

baseline measures of age, gender, mental health status, education, employment, academic status, income, and family composition already being collected by the parent grant.

Aim 2: To examine mediators and moderators of treatment effectiveness and sequencing in order to determine which types and sequence of interventions is best suited for which youth.

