Aim 1: We will randomize **304 participants**; 76 to CM alone, 76 to CM+NH, 76 to CM+ ER, and 76 to CM+NH+ER. Based on the previous work with the SIQ, we believe a 25% reduction among individuals with a score of 30 or greater would represent clinically significant change in suicide ideation.[5] Using pilot data of NH among the WMAT, an average baseline score of 45 could be expected on the SIQ.[5] A clinically significant reduction translates into a large Cohen's D effect size (>0.8). However, we want the power to observe the more moderate effect expected to result from comparing the sequencing of the interventions (NH+ER vs. NH+CM vs. CM+ER vs. CM alone). Using an adjusted alpha to account for multiple comparisons of 0.013, and a correlation of 0.2 among repeated measures, with four groups (NH+ER vs. NH+CM vs. CM+ER vs. CM alone), $n=58$ people per group ($n=116$ randomized at each randomization time-point) would provide 80% power to detect a small to moderate effect (Cohen's $F=0.2$). Adjusting these estimates for 30% attrition would result in $n=76$ per each of the four groups ($n=152$ per arm) for a total sample size of $N=304$.

Please note for our ***the Opioid Data Collection Sub-Study***: We will use a mixed methods approach to examine opioid use among our SMART trial participants through addition of a quantitative opioid related measure and qualitative interviews ($N=30$) with a subset of those who endorse recent or current use.

For the economic evaluation supplement: We will use the same sample of participants as Aim 1. We are not drawing statistical inferences about cost estimates so there is no sample size requirement. Instead, we are reporting on the health care services utilization and costs incurred by study participants before, during and after the intervention. To administer a time use survey and conduct in-person interviews we will use all HUB program case managers (five or more) and healthcare providers (three or more).

For the diversity supplement: We will use a sub-sample of $n=239$ WMAT participants enrolled in the parent trial. This sample size is based on the estimated enrollment rates during the Diversity Supplement study period.

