For the economic evaluation supplement aim: To evaluate healthcare expenditures per participant and intervention we will employ standard two-part regression models used in the analysis of healthcare costs. Variables per claim will include non-identifiable individual study ID, utilization date, charge per claim, and CPT code. Service claims will include all inpatient services and respective length of stay, ED services, outpatient services, specialist care, pharmaceuticals, home health, health transportation, and mental health care utilization and any other health-care related costs. In addition, time use of our staff will be categorized according to the various protocols that they work on. We will estimate the weekly total hours spent in delivering services to youth. The cost of the time allocated to youth services will be estimated by multiplying wage rate for that worker times hours spent delivering services to youth.

We will analyze Celebrating Life Apache surveillance system (CL) data for related data points for study participants, including intake and follow-up case management visits. This data counts the number of times study staff visited or attempted to visit study participants, and is key in accounting for the time and financial costs of conducting study visits with participants.

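### The economic aim hypothesises lower costs than with CM alone, but the sample-size section rules out inference on costs, so the hypothesis cannot be supported or refuted as the plan stands

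*Combined protocol and SAP*

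**What the plan says.** Five places in the combined protocol and SAP bear on this.

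- **Section I, Economic Evaluation Supplement Aim.** The hypothesis is directional and comparative: the effects of NH and ER on ideation and resilience "will reduce participant healthcare and other community and personal costs compared to the standard of care of CM alone".
- **Section II, Background and Rationale.** The trial will "evaluate what are the cost savings per study participant with the implementation of the Southwest Hub interventions", listed as NH, ER, and NH with ER.
- **Section III.A, economic evaluation supplement.** Claims are requested "from one year prior to the study period to 12 months post-enrollment", two years in all per participant.
- **Section III.B, sample size.** "We will use the same sample of participants as Aim 1", followed by "We are not drawing statistical inferences about cost estimates so there is no sample size requirement". The next sentence gives the alternative: "Instead, we are reporting on the health care services utilization and costs incurred by study participants before, during and after the intervention".
- **Section V.C.4, data analysis plan.** "To evaluate healthcare expenditures per participant and intervention we will employ standard two-part regression models used in the analysis of healthcare costs". No contrast, covariate, interval or decision rule is named. Staff time is costed as wage rate times hours.

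Section XI.A only refers back to these sections. Nothing reconciles the hypothesis with the no-inference sentence, and nothing labels the economic aim descriptive. The protocol does use such labels elsewhere: the Aim 2 models are described as hypothesis generating (III.A) and the Aim 3 quantitative data as exploratory (III.B).

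**The concern.** A claim that costs are lower than with CM alone concerns a difference between randomised groups. It needs an estimate of that difference and a statement of its uncertainty. Section III.B disclaims inference and describes a comparison over time instead.

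A comparison over time is open to a specific bias here. Entry requires a qualifying suicidal event in the past 30 days, or release from related inpatient care in that period (IV.A). The year of claims before enrolment therefore contains the index event and any care it led to. A later fall in cost may simply reflect recovery from that event, and could occur with CM alone. The randomised comparison separates the two explanations; a before/after table does not.

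The practical stake is that the Background says the tribal partner wants economic evidence to inform policy and future implementation. A saving quoted without an interval could be taken as firmer than it is.

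**Working it through.** **1. Is there a cost figure to reproduce?** No. The documents give no sample size, power, alpha, standard deviation or effect size for costs. The check is one of consistency, followed by an illustration of precision.

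**2. The statements side by side.**

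| Section | Comparison implied | Uncertainty stated |
|---|---|---|
| I (hypothesis) | NH and ER against CM alone | Not stated |
| II (objective) | Savings for NH, ER, NH with ER | Not stated |
| III.B (sample size) | Before, during, after | Inference ruled out |
| V.C.4 (analysis) | Two-part regression by intervention | Not stated |

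The first two rows need a between-group contrast. The third excludes inference on it. The fourth supplies a model that could estimate it, without naming the contrast.

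**3. Group sizes.** III.B plans 304 participants, 76 in each of four sequences. Each single sequence against CM alone is 76 against 76. Pooling over the other factor (NH against no NH, or ER against no ER) gives 2 × 76 = 152 against 152. The pooled contrasts are not the hypothesis in Section I: the no-NH arm includes those who receive ER, and the no-ER arm includes those who receive NH.

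**4. Precision, with an assumed coefficient of variation (CV).** For a simple difference in means with a common CV, the 95% half-width as a fraction of mean cost is

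1.96 × CV × sqrt(2/n).

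- n = 76: 1.96 × sqrt(2/76) = 0.318 per unit of CV.
- n = 152: 1.96 × sqrt(2/152) = 0.225 per unit of CV.

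| Assumed CV | 76 per group | 152 per arm |
|---|---|---|
| 1 | 32% | 22% |
| 2 | 64% | 45% |
| 3 | 95% | 67% |
| 4 | 127% | 90% |

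These figures take every randomised participant as contributing claims.

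**5. Effect of adjusting for prior-year cost.** The variance falls by a fraction r². With r assumed at 0.3 to 0.5, that is 9% to 25%. The half-width is multiplied by sqrt(1 − 0.09) = 0.95 to sqrt(1 − 0.25) = 0.87, a reduction of about 5% to 13%.

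**6. Timing of ER.** ER is assigned at CM3, 60 days after baseline (V.C.1). Cost counted from enrolment includes about two months that ER cannot have affected. Within the 12-month claims window, about 10 months follow the second randomisation.

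**7. Cost types.** The hypothesis covers healthcare, community and personal costs. The two-part models cover healthcare expenditures. Staff time has a costing formula, and work absenteeism is collected for the costing analysis, but no between-arm analysis is given for either.

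**The case against.** The strongest defence is that the sentence in III.B answers a form item on sample size. Read in that setting, it may mean only that costs are not a powered endpoint, which is reasonable because N is fixed by Aim 1. V.C.4 asks for a brief plan, and it does model expenditure by intervention, so some comparison is evidently intended. This part stands: having no sample-size calculation for costs is not an error, and the proposed text keeps that position. It does not remove the conflict, because the sentence goes further than saying the comparison is unpowered; it disclaims inference.

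Several stronger readings are tempting but unsupported:

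- **That two-part models cannot answer the question.** They can estimate an arm difference with an interval.
- **That costs will be published without any uncertainty, or only as before/during/after tables.** No section says that intervals will be withheld; V.C.4 neither promises nor forbids them.
- **That prior-year claims will not be used as a covariate.** V.C.4 lists no covariates either way.
- **That costs will fall in every arm after enrolment.** Ideation alone can qualify for entry, all arms are referred to care, and NH encourages treatment uptake, which could raise claims. A fall may occur; it is not certain.
- **That a saving of 20% to 40% could never be told from zero.** That depends on the CV. At an assumed CV of 1, an observed 40% saving exceeds the half-width even at 76 per group (32%).

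It is also fair to say that rewording the hypothesis as a descriptive objective would remove the contradiction. It would, but it would leave unused a randomised comparison that the planned data and model can already provide.

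**Conclusion.** The conflict is real and is stated in the text, not inferred from missing detail. Sections I and II set a directional cost hypothesis against CM alone and promise savings per participant; III.B rules out the inference needed to judge either. The hypothesis is therefore unanswerable under that rule, although the planned model could address it.

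On assumed CVs of 1 to 4, the 95% half-width is about 32% to 127% of mean cost for the comparison with CM alone and 22% to 90% for the pooled contrasts. These ranges rest on the assumed CVs, a simple difference in means and complete claims; the interval from the two-part model could differ. They show that the comparison is likely to be imprecise, which is a reason to report the interval.

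The point is minor for the trial as a whole. It concerns a supplement and does not touch the analyses of suicidal ideation or resilience.

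**What to change.** Replace the no-inference sentence in III.B with wording such as:

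> No sample size was set for costs; cost comparisons are exploratory and unpowered. Between-sequence differences in healthcare cost against CM alone (NH, ER, NH+ER), and pooled NH vs no NH and ER vs no ER, will be estimated from the two-part model, adjusted for prior-year cost, with bootstrap 95% confidence intervals. For the pooled ER contrast, costs are counted from the second randomisation (CM3). Savings will be reported only with these intervals.

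Repeat the contrasts and the covariate in V.C.4, and keep the before/during/after tables as description. In Section I, limit the hypothesis to the cost types that are analysed; as it stands, the two-part models support a statement about healthcare expenditure only.

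The cost is redrafting and a bootstrap. The claims are already requested and the model is already planned, so no visit, data item or participant is added. The downside is that wide intervals will show how uncertain any saving is.

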Aim 3: Study participants will be 25-50 key stakeholders including youth, caregivers, program providers, community members, tribal leaders, and other researchers across the Hub, including satellite partners. Sample size for Aim 3 is based on qualitative research theory on saturation, a point after which common themes and information from respondents tend to converge. Quantitative data collected is exploratory in nature and will be used to help inform future implementation and scale-up of the programs.

Please note for our ***the Opioid Data Collection Sub-Study***: Key stakeholders will only be asked about opioid use generally in relation to the community, not their personal use. However, we are aware that personal use may still be disclosed. We will use the same referral and follow-up procedures for these participants as those in our SMART trial. We estimate 25 participants based on the number of Hubs sites and advisory board members.

IV. Participants:

Describe the study participants and the population from which they will be drawn. Specify the inclusion and exclusion criteria. If you plan to include children, note their ages and whether you will include children in foster care.

Note if the participants are particularly vulnerable in terms of cognitive limitations, education, legal migration status, incarceration, poverty, or some combination of factors.

Aim 1: Study participants will be self-identified Native Americans who are between the ages of 10 and 29 years old and reside on or near the Fort Apache Indian Reservation and are identified in the existing surveillance and case-management (CM) system as having recently had a validated suicide attempt, ideation, or binge substance use episode and recent ideation. The majority of these tribal populations lives below the federal poverty line. The economic evaluation supplement does not involve any contact with the study participants.

A. Inclusion Criteria:

- Native American youth ages 10 to 29 years old.
- Reside on or near the Fort Apache Indian Reservation.
- Parent/guardian consent for youth under 18 years old.
- Suicide ideation, binge substance use with recent (i.e. within the last 3 months) suicide ideation, or suicide attempt in the past 30 days as identified and verified by the surveillance system OR release from inpatient care related to suicide ideation or attempt within past 30 days

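### The pre-enrolment claims year contains the index episode, yet the plan neither ties cost savings to the randomised comparison nor says what the two-part cost models adjust for

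*Combined protocol and SAP*

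**What the plan says.** - **Claims window (III.A, economic evaluation supplement).** Claims are requested for each participant "from one year prior to the study period to 12 months post-enrollment--for a total of 2 years of participant claims data".
- **Entry (IV.A Inclusion Criteria).** Youth qualify through ideation, a binge episode with recent ideation, or a "suicide attempt in the past 30 days as identified and verified by the surveillance system". The alternative route is "release from inpatient care related to suicide ideation or attempt within past 30 days". Section V.B.1.c describes the same 30-day limits.
- **Output (III.B, economic evaluation supplement).** Inference on cost is disclaimed, no sample size is set for it, and the stated product is that "we are reporting on the health care services utilization and costs incurred by study participants before, during and after the intervention".
- **Objective (II).** The study will "evaluate what are the cost savings per study participant with the implementation of the Southwest Hub interventions". New Hope (NH), Elders' Resilience (ER) and the two together are listed. No comparator is named.
- **Hypothesis (I, Economic Evaluation Supplement Aim).** NH and ER are expected to lower costs relative to CM alone.
- **Model (V.C.4).** For expenditure by participant and intervention, "we will employ standard two-part regression models used in the analysis of healthcare costs". The claim fields are listed (study ID, date, charge, procedure code). No covariates, form of arm contrast, outcome period or handling of the index episode is given. The same section does state adjustment variables, gender and age, for the diversity supplement's models.

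**The concern.** Participants are selected just after a crisis, and the year leading up to that selection serves as the 'before' period. Mean cost would then tend to fall afterwards even if no intervention worked, which is ordinary regression to the mean plus a one-off index cost. Section III.B makes the before/during/after description the main product, and section II asks for savings without saying savings against what. A reader could therefore take the fall within the NH, ER or NH+ER groups as money saved. Section II says the tribal partners want the economic results for policy decisions, so such a misreading would matter.

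The second strand is smaller. A year of pre-enrolment claims is being obtained for everyone, but the plan does not say whether it enters the two-part models. If it does not, some precision in the randomised cost comparison may be given up for nothing.

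**Working it through.** **1. The window.** 12 months before + 12 months after = 24 months, which reproduces the stated 2 years. It does so only if both halves are anchored at enrolment. Read literally, the study period is not a per-participant date.

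**2. Where the index episode falls.** The qualifying event, or the discharge, lies 0 to 30 days before enrolment. An admission precedes its discharge. Recent ideation on the binge route may reach back 3 months, which is still inside the 12. The index episode is thus in the 'before' year for essentially everyone and cannot be in the 'after' year.

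**3. Before/after change with no treatment effect.** Let B be background cost per year, C the cost of one acute event, p the share whose index event generates a claim, and q the share with a costed event in the following year.

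Before = B + pC; after = B + qC; relative change = (q − p)C / (B + pC).

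The documents give none of these. Assumed ranges: B 2,000 to 4,000, C 2,000 to 10,000, p 25% to 100%, q 0% to 40%.

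| B | C | p | q | Before | After | Change |
|---|---|---|---|---|---|---|
| 2,000 | 10,000 | 100% | 0% | 12,000 | 2,000 | −83% |
| 2,000 | 5,000 | 50% | 20% | 4,500 | 3,000 | −33% |
| 4,000 | 5,000 | 50% | 20% | 6,500 | 5,000 | −23% |
| 4,000 | 2,000 | 25% | 20% | 4,500 | 4,400 | −2% |
| 2,000 | 10,000 | 25% | 40% | 4,500 | 6,000 | +33% |

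The first and last rows are the extremes over the whole range. Cost falls when p > q and rises when q > p.

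**4. The randomised contrast.** With no effect, every arm has the same expected after-year cost, B + qC, so the expected difference from CM alone is zero whatever p is. A simulation with no effect used four groups of 76, p = 50%, q = 20%, a logit-plus-gamma two-part model, and 500 runs in each of three settings of between-person variation.
- Mean cost fell by 31% to 41% in every arm.
- All four arms fell together in 80% to 98% of runs.
- The average unadjusted between-arm estimate was 17, 44 and −8, against single-trial standard errors of 407, 456 and 787. Dividing by √500 gives simulation errors of about 18, 20 and 35. One estimate is about two simulation errors from zero and the signs are mixed, so there is no consistent bias.

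**5. Value of adjusting for pre-enrolment cost.** In a linear approximation, variance is multiplied by 1 − r², where r is the correlation of prior-year with later cost (assumed; not in the documents). N = 304 then behaves like 304/(1 − r²). The detectable difference for 76 against 76 at two-sided 0.05 and 80% power is (1.96 + 0.84) × √(2/76) = 0.454 SD unadjusted, multiplied by √(1 − r²) after adjustment.

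| r | Variance factor | SE reduction | Equivalent N | Detectable difference (SD) |
|---|---|---|---|---|
| 0.1 | 0.99 | 0.5% | 307 | 0.452 |
| 0.2 | 0.96 | 2% | 317 | 0.445 |
| 0.3 | 0.91 | 5% | 334 | 0.434 |
| 0.5 | 0.75 | 13% | 405 | 0.394 |

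In the simulated two-part model, adjusting for log prior-year cost multiplied the SE by 1.00, 0.99 and 0.91 at correlations of 0.02, 0.07 and 0.22. The linear factor at 0.22 would be √(1 − 0.048) = 0.98, so the approximation is only a guide.

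**The case against.** The case on the other side is substantial.

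- The supplement is presented as descriptive. No passage calls a before/after fall a saving. Section I names CM alone as comparator, and listing only the three active options in section II fits CM alone as the implied reference. A fall common to all arms cancels in that contrast.
- V.C.4 answers a template item that asks for a brief plan, and silence on covariates is not exclusion. Prior-year cost can be derived from the dated claims.
- A fall is not assured. By the definitions in IV.A, ideation alone qualifies, aborted and interrupted attempts count as attempts, and a binge episode can qualify without emergency care, so an index event may leave no claim. All youth are referred to care, NH encourages treatment uptake, and V.C.1 chose the follow-up as a period of high risk of further events. Each of these can raise later cost.
- A one-off index cost lowers the correlation between years, and event type, already a stratification factor, may carry part of the same information.

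All of this stands, and it rules out several stronger readings. A reader might infer that the models omit prior-year cost, but the plan does not say so. A reader might infer that every arm is bound to show savings, but that needs p > q. A reader might infer that the comparison with CM alone is biased, but it is not. Nor do the documents show that prior-year cost predicts later cost strongly.

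What does not stand is the idea that a descriptive label suffices. Section III.B's stated product is the before/during/after description, section II's savings objective has no comparator, and nothing warns against reading one as the other. Disclaiming inference on cost also sits badly with a directional hypothesis in section I and regression models by intervention in V.C.4.

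**Conclusion.** The point holds as a gap in specification, not as a demonstrated error in the randomised analysis. By design the index episode sits in the pre-enrolment year, so the planned before/after figures are likely, but not certain, to fall in all arms, CM alone included, without any treatment effect. The size is unknown. It depends on the shares of index and later events that generate claims and on background cost; −83% to +33% spans the assumed inputs, and no single figure in it is an estimate for this trial.

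The contrast with CM alone is unbiased with or without adjustment. The gain from adjusting is also unknown and may be small: about 1% to 4% of variance at correlations of 0.1 to 0.2, 9% at 0.3 and 25% at 0.5. The change is worth making because it prevents a misleading reading of a planned output and uses data already requested.

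**What to change.** 1. In sections II, III.B and V.C.4, define cost savings only as the randomised between-arm difference in post-enrolment claims. Label before/during/after figures descriptive and always show CM alone beside the other arms. Reconcile the disclaimer of cost inference in III.B with the hypothesis in section I and the models in V.C.4.
2. In V.C.4, list the covariates for both parts of the two-part model: 12-month pre-enrolment cost with an any-use indicator, age group and event type. Use the age grouping actually applied at randomisation, since V.C.1 and V.C.5.A give different groupings.
3. Report index-episode claims (index date to enrolment) separately from the rest of the pre-enrolment year, and state in III.A that both halves of the claims window are anchored at enrolment.

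The cost is wording and analysis code. Both years of claims are already requested, so no added data, participant contact or sample size is needed.
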